Based on the randomised trials showing benefit of radiotherapy with combined hormone- and radiotherapy compared to hormone therapy only (9,13,14), 3 months pre-irradiation castration is standard for high-risk patients in many institutions (7). Studies have addressed weakening MRI signals and PSMA PET-uptake after castration (60,61). However, there is not enough data to guide us to the optimal imaging to define intra-prostatic lesions in patients who are treated with a combination

of medical castration and radiotherapy. Currently this topic is being investigated in a phase 2 study (Danish Ethical Committee 2303938), conducted by the research group to prepare for the present study.

Additional improvements in delivery, such as MRI based image guidance, improved CT based image guidance, or adaption of the daily dose plan to the anatomy of the day etc. may improve outcomes further (58,62). If participating centers implement follow local adaptive strategies for adaptation due to anatomical changes, the center must document the procedures.

Study design

Statistical considerations

The reference schedule is 20 fractions, 5 fractions per week, without boost. For this reference schedule we assume the following outcomes of relevance to the statistical sample size calculation:

- 5-year biochemical control: 87%
- 5-year freedom from distant metastasis: 90% with sensitivity analysis 85%-90% 5 year OS: 82%.
- Prevalence of grade 2 or worse gastrointestinal(GI) toxicity: 10% at ~1 year
- Prevalence of grade 2 or worse genitourinary(GU) events: 20% at ~1 year

Dropout is assumed to be dominated by death from other causes. The expected OS of 82% yields a dropout rate of $\eta=0.039$ when assessing endpoints where death is a competing event (Such as freedom from distant metastasis). We account for this dropout in the calculations below.

Table showing overall design

		Fractionation trial Trial tests for non-inferiority of short fractionation	
		12 fractions	20 fractions
Boost trial Trial tests for superiority of focal boost	Boost	Boost: 60 Gy/12 fractions (EQD2=110 Gy) Prostate: 50 Gy/12 fractions (EQD2=80 Gy) Pelvic: 37 Gy/12 fractions (EQD2=48 Gy)	Boost: 75 Gy/20 fractions (EQD2=110 Gy) Prostate: 60 Gy/20 fractions (EQD2=77 Gy) Pelvic: 45 Gy/20 fractions (EQD2=48 Gy)
	No boost	Prostate: 50 Gy/12 fractions (EQD2=80 Gy) Pelvic: 37 Gy/12 fractions (EQD2=48 Gy)	Prostate: 60 Gy/20 fractions (EQD2=77 Gy) Pelvic: 45 Gy/20 fractions (EQD2=48 Gy)

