- Dose constraints for organs at risk are kept according to guidelines in this protocol
- Guidelines for IGRT according to institutional protocol.
- Treatment is delivered with institutional protocols that fulfil the goals and constraints given in this protocol (appendix B).

Radiotherapy

Radiotherapy planning:

Modern RT planning is wholly dependent on high level computing. This allows for creation of highly personalised dose plans with several different dose levels within the same plan. Additionally, these plans exhibit sharp dose gradients towards critical organs at risk (OAR). Depending on treatment modality plans will either use a simultaneously integrated or sequential boost. In the former case the treatment session delivers a boost to the intraprostatic lesion (if randomised for boost) in addition to the prescribed doses to prostate and elective targets. In the latter case prescribed doses to prostate and elective targets are delivered in the same treatment sessions whereas a boost will be delivered in separate sessions using specialised equipment e.g. an MR-Linac. In either case the dose planning will seek to minimise the trade-off between sufficient target coverage - usually between 95% and 107% of the prescribed target doses - and reducing as much as possible the doses to OAR. It is not uncommon that requirements for target and OAR doses are mutually exclusive. The order in which every dose requirement should be prioritised is detailed in Appendix B as well as specific

requirements to target coverage. To ensure that the dose planning of all participating centres will be vetted as part of the comprehensive RT-QA program described in Appendix A.

Rectal and bladder preparation protocol:

Patients should be treated with a comfortably filled bladder and an empty rectum/bowel according to local protocol. Use of Image Guided Radiotherapy (IGRT) is mandatory to ensure the elective target coverage and to assess bladder- and rectal filling. Application of a bladder-filling protocol in an attempt to decrease the volume of bladder irradiated is recommended using IGRT to check the target positioning.

Target volume definition, dose and fractionation:

Delineation of the targets are performed on the treatment planning MRI, guided by both the diagnostic multiparametric MRI (mpMRI) and PSMA-PET CT scan. Organs at risk (OARs) are delineated on the planning CT scan.

Fractionation:

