- 20 fractions, no boost: Prostate and seminal vesicles: 60 Gy/ 20 fractions. Pelvic: 45 Gy /20 fractions.
- 20 fractions, boost: Boost 75 Gy/20 fractions, prostate and seminal vesicles: 60 Gy/ 20 fractions. Pelvic: 45 Gy /20 fractions.
 - If a boost is delivered on special equipment, such as an MR accelerator, it is allowed to give the boost in fewer fractions with same equivalent dose and maintaining same overall treatment time
- 12 fractions, no boost: Prostate and seminal vesicles: 50 Gy/ 12 fractions, Pelvic: 37 Gy /12 fractions.
- 12 fractions, boost: Boost 60 Gy/12 fractions, prostate and seminal vesicles: 50 Gy/12 fractions, Pelvic: 37 Gy /12 fractions.
 - If a boost is delivered on special equipment, such as an MR accelerator, it is allowed to give the boost in fewer fractions with same equivalent dose and maintaining same overall treatment time

All treatments with 5 fractions per week

Intraprostatic lesion(s): If a boost is to be performed, the most dominant lesion(s) are contoured as GTVp_FB_post with the prefix 1, 2 etc. according to the number of lesions with the use of information from the planning MRI and PSMA-PET/CT used as guidance. As the lesions and the prostate gland normally decrease in size with neoadjuvant ADT, a CTVp_FB_final should be created. This volume should not only include the GTVp_FB_post but also account for the potential initial tumor volume (GTVp_FB_pre) as observed on the diagnostic MRI performed prior to initiating ADT. The three sequences used from mpMRI are:

- 1) T2 weighted image, where the tumour lesions appear in grey
- 2) DWI (Diffusion Weighted Imaging), where the tumour lesions appear as white areas
- 3) ADC (Apparent Diffusion Coefficient), where the tumour lesions appear as black areas

CTVp_FB should be included in the CTVp or CTVp_SV. No margin is used for intraprostatic lesions.

For radiation target nomenclature, see appendix C

Prostate: MRI is used to contour the CTVp volume as the whole gland with any visible extracapsular extension of disease included.

Elective pelvic lymph nodes: If N1, elective lymph nodes should be delineated according to NRG Oncology Updated International Consensus Atlas on Pelvic Lymph Node Volumes for Intact and Postoperative Prostate Cancer, 2021 (74). Elective pelvic lymph node area is named CTVn_E. Any clinically suspicious lymph nodes should be included in the CTVn_E. PTV is derived by adding a 5-10mm margin to CTVp, CTVp_SV and CTVn_E. See appendix D

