Seminal Vesicles (SV): If T3b disease, the entire seminal vesicle volume bilateral should be included in the CTVp_SV and treated to a high dose. If \leq T3a, only the proximal 2 cm of the seminal vesicle bilateral should be included in the CTVp_SV and treated to an elective dose. See appendix E

Organ at risk (OAR): will be contoured according to national guidelines.

Organs at risk

The prostate is situated adjacent to both the rectum and urinary system which risks gastro-intestinal (GI) and genitourinary (GU) adverse effects. The FLAME trial showed that long term side effects of conventional prostate RT even when combined with a mildly fractionated intra-prostatic boost are generally modest in frequency and severity (28). However, the addition of an extremely hypofractionated boost close to organs at risk approaches the realm of brachytherapy where very high point doses directly adjacent or even in the organ can lead to very severe adverse effects. The HypoFLAME trial (75) demonstrated that such an approach leads to only low frequencies of grade 2 side effects and very rarely grade 3. The results rely on the treatment being isotoxic i.e. maintaining pre-existing dose constraints of equivalent dose in the specific hypofractionated scheme. Table 1 in appendix B details the isotoxic dose constraints for the relevant organs at risk for each trial arm while Table 2 details the requirements for target coverage.

Study procedures

Identification and information of eligible patients

Eligible patients will be identified and discussed by doctors at the regional multidisciplinary team conference (MDT). Data from the medical record for eligibility screening are handed over to the researcher (name and CPR number of patients to receive radiotherapy, and diagnosis, i.e. cancer of the prostate/DC61.9). Other study relevant data are retrieved only after written consent. All patients

referred for RT who meet the inclusion criteria will be recorded on a screening list. Neoadjuvant and adjuvant ADT will follow Danish national guidelines, which currently include 3 months LHRH agonist or antagonist prior to the start of radiotherapy

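### The fewer-fraction boost option preserves equivalent dose, but Appendix B fixes physical doses for 20 and 12 fractions only, so for most session counts the two rules give different lesion doses and the organ limits are no longer isotoxic

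*Protocol*

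**What the plan says.** - **The option.** In the fractionation list under Target volume definition, dose and fractionation, both boost arms carry the same sub-item for boosts on dedicated machines (an MR accelerator is its example). The sub-item reads: "it is allowed to give the boost in fewer fractions with same equivalent dose and maintaining same overall treatment time". It gives no number of sessions and no α/β. The list closes with "All treatments with 5 fractions per week".
- **How it is delivered.** Radiotherapy planning says that, when the boost is not integrated, "a boost will be delivered in separate sessions using specialised equipment e.g. an MR-Linac".
- **The intended equivalent dose.** The design table under Statistical considerations lists "Boost: 75 Gy/20 fractions (EQD2=110 Gy" and "Boost: 60 Gy/12 fractions (EQD2=110 Gy", each closing its bracket there. The prostate doses are 60 Gy/20 (EQD2 77) and 50 Gy/12 (EQD2 80).
- **The binding dose rules.** Treatment related procedures requires institutional protocols to meet the goals and constraints of Appendix B. Table 2 there sets the lesion mean at 75 or 60 Gy within 1%, and V71.25Gy or V57Gy above 99.5%, in columns for 20 and 12 fractions. Table 1 gives organ limits to apply as physical doses for the same two schemes. It also has an EQD2 column, at α/β 3.
- **The safety principle.** Organs at risk says that the low toxicity seen with such boosts relies on "maintaining pre-existing dose constraints of equivalent dose in the specific hypofractionated scheme".

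**The concern.** In the linear-quadratic model, moving the boost into fewer sessions at the same equivalent dose changes the physical total. A site using the option therefore has two instructions for the lesion, one on each scale, and nothing says which prevails. Table 2's priority column does not help: it ranks targets against organs, not one dose scale against another.

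Boost dose is the randomised factor. The option is tied to equipment, and so probably to centre. The protocol plans to test whether the boost effect on biochemical control differs between MR-linac, CT-based and proton techniques. If technique also determines which dose rule was followed, that test mixes technique with dose. The organ limits raise the same question, because a physical limit derived for equal fractions does not carry the same EQD2 when part of the dose arrives in a few large sessions.

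**Working it through.** **Inputs.** Doses, fraction numbers and stated EQD2 values come from the design table; tolerances, limits and organ α/β = 3 from Appendix B. The range of 1 to 5 boost sessions is an assumption, since the protocol says only that there are fewer. All totals below are arithmetic tests, not proposed doses.

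**Step 1: reproduce the stated EQD2.** EQD2 = D(d + α/β)/(2 + α/β). With α/β = 1.6:

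| Schedule | Computed | Stated |
|---|---|---|
| 75 Gy/20 | 111.5 | 110 |
| 60 Gy/12 | 110.0 | 110 |
| 60 Gy/20 | 76.7 | 77 |
| 50 Gy/12 | 80.1 | 80 |
| 45 Gy/20 | 48.1 | 48 |
| 37 Gy/12 | 48.1 | 48 |

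Five of six agree on rounding and the sixth is 1.3% high, so about 1.6 is a fair inference. At α/β = 3 the two boost schedules give 101 and 96 Gy, which does not reproduce 110.

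**Step 2: hold each arm's own EQD2 and solve for the physical total.** Let N be the planned fractions, b the prostate dose per fraction (3 Gy or 4.17 Gy) and k the boost sessions.
- Separate sessions of size y: N·b(b + 1.6) + k·y(y + 1.6) = 3.6 × EQD2.
- Extra dose x within k planned fractions: (N − k)·b(b + 1.6) + k·(b + x)(b + x + 1.6) = 3.6 × EQD2.

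Example, 20-fraction arm, 5 separate sessions: y(y + 1.6) = (111.46 − 76.67) × 3.6/5 = 25.05, so y = 4.27 and the total is 60 + 5 × 4.27 = 81.3 Gy.

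| k | 20 fr, separate | 20 fr, within | 12 fr, separate | 12 fr, within |
|---|---|---|---|---|
| 1 | 70.4 | 68.0 | **59.6** | 56.5 |
| 2 | **74.3** | 70.0 | 63.2 | 57.8 |
| 3 | 77.1 | 71.1 | 65.7 | 58.4 |
| 4 | 79.4 | 71.9 | 67.8 | 58.9 |
| 5 | 81.3 | 72.4 | 69.5 | 59.2 |

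The Table 2 windows are 74.25–75.75 Gy and 59.4–60.6 Gy; bold entries fall inside. The deviations run from about −9% to +8% and from −6% to +16%. A boost on most planned fractions also fits (15 of 20 gives 74.6 Gy; 8 of 12 gives 59.7 Gy). At α/β = 3 the ranges are 68.4–80.6 and 56.7–68.3 Gy, and within k = 1 to 5 the same two cases fit. If the printed 110 Gy is held instead of 111.5 in the 20-fraction arm, 2 separate sessions give 74.0 Gy, just outside.

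V71.25Gy > 99.5% forces a mean of at least 0.995 × 71.25 = 70.9 Gy, so the 68.0, 70.0 and 70.4 Gy cases fail that goal too.

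**Step 3: hold the physical 75 Gy, with the extra 15 Gy in 5 sessions of 3 Gy (α/β 1.6).**
- Separate: 76.67 + 15 × 4.6/3.6 = 95.8 Gy EQD2.
- Within planned fractions: 45 × 4.6/3.6 + 30 × 7.6/3.6 = 120.8 Gy EQD2.
- Reference, 75 Gy/20: 111.5 Gy.

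**Step 4: Table 1, urethra D0.1ccm, 71 Gy in the 20-fraction column (α/β 3), assuming 60 Gy in 3 Gy fractions plus 11 Gy with the boost.**
- 20 equal fractions: 71 × 6.55/5 = 93.0 Gy EQD2. The EQD2 column lists 88, so a gap exists before the option is used.
- Within 1 planned fraction: 57 × 6/5 + 14 × 17/5 = 116.0; within 2, 103.9; within 5, 96.6.
- 1 separate session: 60 × 6/5 + 11 × 14/5 = 102.8; 2 sessions, 90.7; 5 sessions, 83.4.

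**Step 5: timing.** At 5 per week, 20 fractions take 4 weeks and 12 take 2.4. Separate sessions on top of these lengthen the course unless two sessions share a day, which the protocol does not address. A boost within planned fractions breaks neither timing rule but is not the separate-session delivery described in Radiotherapy planning.

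**The case against.** The best defence is that the option is a specific exception to a general default. Table 2's columns are headed 20 and 12 fractions, the intended EQD2 of 110 Gy is printed for both boost arms, and Table 1 has an EQD2 column with its α/β, so a physicist could convert. Safeguards also exist: the first boost patient in each regimen at each centre is reviewed before treatment, every centre passes a boost dummy run, and dose and fractionation are recorded. Randomisation is stratified by centre, so centre technique does not confound boost against no boost. The technique comparison is secondary and not randomised.

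Most of this stands, and it rules out three stronger readings that a reader might draw.
- That the rules can never be met together: some session counts meet both.
- That these patients have no boost dose or organ limit at all: the intended EQD2 and a basis for conversion are printed.
- That the physical organ limits are always too loose: with 2 to 5 separate sessions the urethral limit is stricter than over 20 equal fractions.

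Using 3 for organs and another value for tumour is also no contradiction. What the defence does not supply is any text exempting the option from Appendix B, instructing the conversion, or giving the tumour α/β. The early plan review has no stated rule by which to judge such a plan.

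**Conclusion.** The conflict holds for most session counts, not all. At unchanged EQD2 and 1 to 5 boost sessions, the lesion total runs from 68.0 to 81.3 Gy or 56.5 to 69.5 Gy, against a tolerance of 1% around 75 or 60 Gy. A site that keeps 75 Gy in 5 sessions delivers 95.8 or 120.8 Gy EQD2, against 111.5. Table 1's physical limits are not isotoxic for this delivery and can err either way: for the urethral example, 83 to 116 Gy EQD2, against 93 over equal fractions and 88 listed. The timing conflict arises only if separate sessions fall on extra days.

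The lesion figures rest on the linear-quadratic model, an inferred α/β of about 1.6 and the assumed 1 to 5 sessions; the lesion pattern barely changes at α/β 3. The protocol does not say how many patients would use the option, so its effect on the primary comparison cannot be sized. Because it concerns the dose under test and organ limits that the protocol itself treats as the basis for safety, it needs resolving before any centre uses the option.

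**What to change.** Reconcile the design table, Treatment related procedures, Radiotherapy planning, the fractionation list, Organs at risk and Appendix B, so that:
- one stated rule governs the boost objective and the organ limits when the option is used, and Appendix B says how its values apply to such plans;
- the α/β that defines the equivalent dose is stated;
- the text explains how separate sessions fit the five-per-week rule and the unchanged overall time;
- boost technique and number of boost sessions are recorded per patient, alongside the dose and fractionation data already collected. The planned EQD2 dose-response analysis needs the session count too.

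Which scale and values apply is for the sponsor to decide. The cost is protocol wording, one or two data fields, and an EQD2 plan sum at sites that use the option.

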The side effects of ADT are well documented and an integral part of daily clinical practice in the treatment of PCa patients. The expected side effects of ADT will be documented via the PROM questionnaires filled in by the patients at each follow-up visit. They will not be recorded continuously as adverse events (AE).

Boost to prostate and the hypofractionation schedule in the protocol are the new parameters being examined in the study and any AE and serious adverse events (SAE) will be reported continuously.

The local investigator is responsible for assessing the causality of all AE and SAE in relation to the trial therapy.

Adverse Event (AE)

Any unfavourable and unintended (acute or chronic) symptom related to the organs in the pelvic and abdomen and caused by radiotherapy:

Urogenital: urinary incontinence, urinary retention, urgency, increased urinary frequency, irritative urinary symptoms, bladder spasm, pain, hematuria, urinary tract obstruction, urinary fistula.

Gastrointestinal: Incontinence for gas/liquid or solid stool, diarrhea, inability to defer defecation, increased number of daily defecation, abdominal pain, rectal bleeding, rectal fistula.

Any condition that exists when the patient is included in the study will be recorded as Medical History. However, it must be reported as an AE if the condition deteriorates during the trial.

AEs are recorded in the eCRF.

Serious Adverse Event (SAE)

A SAE is a radiotherapy related serious event, which may be caused by radiotherapy, occurring during radiotherapy and in the follow-up, which results in any of the following: death, a life-threatening experience that requires hospitalization or requires intervention to prevent permanent impairment/damage.

SAEs are recorded in the SAE eCRF

A detailed description of the AE and SAE will be collected and include the time of onset, grade and severity, management and treatment of the side effect, the outcome, the time to resolution or stabilization and consequence for the RT treatment. All AEs and SAEs occurring during the study must be systematically documented, irrespective of their causal relationship to the treatment

The AEs and SAEs will be followed until resolved or considered stable or until it has been established that participation in the study was not the cause. They will be evaluated by the local site investigator and reported to the trial management committee.

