During follow-up after radiotherapy (up to 60 months), all radiation-induced SAE will be reported and followed.

Due to the severity of the disease in this study, the following situations are excluded from expedited notification on a SAE form and should instead be reported in the Case Report Form (CRF) follow-up form.

- Elective hospitalisation to simplify treatment or procedures
- Elective hospitalisation for pre-existing conditions that, in the investigator's opinion, have not been exacerbated by trial treatment

- Disease progression
- Death as a result of disease progression

All SAE must be reported to sponsor within 1 working day.

Sponsor reports all SUSARs (Suspected Unexpected Serious Adverse Reactions) to the Ethics Committee within 7 days, if life threatening or fatal, and within 15 days, if not life threatening. Sponsor will annually report all SAEs to the Ethics Committee.

Endpoints

Primary endpoint

- Freedom from distant metastasis (FFDM)

Secondary endpoints

- Freedom from biochemical relapse
- Time to salvage hormonal therapy
- Regional relapse-free survival (rRFS)
- Local relapse-free survival (rRFS)
- Overall survival (OS)
- Prostate cancer specific survival
- Self-reported quality of life (QoL)
- Toxicity as CTCAE

Disease related endpoints are calculated from randomisation to event.

Recommended work-up at suspected recurrence

Diagnostic workup on suspicion of recurrence takes place according to national guidelines as described below.

PSMA PET/CT is recommended:

- If a recurrence is suspected biochemically according to the Phoenix criteria
- If a recurrence is suspected clinically, e.g: Bone pain, anemia, urinary symptoms
- If recurrence is suspected by radiographic test

If PSMA PET/CT shows no sign of regional or distant metastases, a diagnostic mpMRI of the prostate is recommended. Local recurrence after definitive radiotherapy should be confirmed by biopsy from the site of suspected recurrence if the result has implication for the treatment.

Cancer related endpoints

Events are: occurrence of distant metastases, castration resistance, biochemical relapse as defined by Phoenix criteria (PSA nadir + 2) (76), start of endocrine treatment, local recurrence, regional recurrence, and death.

Distant metastasis

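### The AE and SAE sections give incompatible rules on whether causation by radiotherapy is a condition for recording an event

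*Protocol*

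**What the plan says.** Under Adverse Events (AEs) and Serious Adverse Events (SAEs), the protocol names the boost and the hypofractionated schedule as what is new and says that AEs and SAEs are reported continuously. It adds: "The local investigator is responsible for assessing the causality of all AE and SAE in relation to the trial therapy".

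The section Adverse Event (AE) defines an AE as an unwanted "symptom related to the organs in the pelvic and abdomen and caused by radiotherapy". Lists of urogenital and gastrointestinal symptoms follow. A condition present at inclusion becomes an AE if it gets worse during the trial, and no cause is required for that.

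The section Serious Adverse Event (SAE) begins: "A SAE is a radiotherapy related serious event, which may be caused by radiotherapy", followed by the seriousness criteria. It then states: "All AEs and SAEs occurring during the study must be systematically documented, irrespective of their causal relationship to the treatment". Events are followed until resolved or stable, or "until it has been established that participation in the study was not the cause". For the period after radiotherapy, up to 60 months, the wording is that "all radiation-induced SAE will be reported and followed".

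**The concern.** Causation appears in two roles that cannot both hold. In the definitions it is a condition of entry: an event not caused by radiotherapy is not an AE. In the documentation rule it is irrelevant to entry and is assessed afterwards. Sites can follow either rule and point to the protocol in support.

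The entry rule fixes which safety events the database can ever hold. If attribution comes first, an event judged unrelated leaves no trace, so it cannot be re-adjudicated or included in a sensitivity analysis. The person judging is the local investigator. The protocol does not use the term open-label, but 12 versus 20 fractions is visible to anyone treating the patient. The only blinding described, under Pre-planned analyses during accrual, covers the dose-response analysis. That the judgement is made knowing the arm is therefore an inference, though a strong one.

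**Working it through.** No arithmetic applies, because the protocol gives no figure for attribution or for AE counts. The check is whether the sentences can be read together.

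**The rules side by side**

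| Place | Link to radiotherapy needed for the event to count |
|---|---|
| AE definition | Caused by it |
| SAE definition | Related to it, and in the same sentence possibly caused by it |
| Documentation rule (SAE section) | None |
| Worsening of a pre-existing condition (AE section) | None stated |
| SAEs after radiotherapy, up to 60 months | Radiation-induced |

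**Can the documentation rule mean all AEs as defined above?** Then every AE is already caused by radiotherapy, and the instruction to disregard causal relationship has nothing to act on. Four other provisions also make sense only if unrelated events are recorded:

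1. The local investigator assesses causality of all AEs and SAEs. For AEs this is redundant if causation was the entry condition.
2. Follow-up of an event may end once study participation is shown not to be the cause. Such an event must have been entered without that question settled.
3. Worsening of a pre-existing condition is reportable whatever the cause.
4. Disease progression, death from it, and elective admission for pre-existing conditions not made worse by trial treatment are expressly exempted from expedited SAE notification. If SAEs had to be radiotherapy related, most of these exemptions would be unnecessary.

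**Two hypothetical events**

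- Diarrhoea in the second week, which the investigator puts down to an infection. It is on the symptom list. Under the AE definition it is not entered. Under the documentation rule it is entered and marked unrelated.
- Life-threatening rectal bleeding with admission at month 30, judged possibly but not probably due to radiotherapy. It meets the possibility wording of the SAE definition. Whether it is radiation-induced is open.

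The same facts give different records depending on the sentence followed.

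**Which data are exposed**

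- The visit schedule under Follow-up and Data Collection marks CTCAE and questionnaires at month -1 and at months 3, 15, 27 and 63. No attribution condition is stated for either, so this stream lies outside the conflict.
- At 5 fractions per week, treatment lasts 12/5 = 2.4 weeks or 20/5 = 4 weeks. No CTCAE or questionnaire visit falls in that period. Continuous AE/SAE reporting is the only toxicity reporting the protocol prescribes for it, apart from side effects taken from the medical record.
- SAE reports to the sponsor within 1 working day, and the annual SAE report to the Ethics Committee, can contain only what the entry rule lets through.

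**The case against.** The strongest defence is that two different causes are meant. All four arms receive radiotherapy, and causality is assessed against the trial therapy, which could mean the boost and the short schedule. An event could then be caused by radiotherapy, and so be an AE, yet not be due to the trial therapy. That would give the documentation rule some content. The reading is possible but strained. The rule refers only to the treatment, without defining it, and the deterioration rule and the SAE exemptions still presuppose that unrelated events are recorded.

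Several other points stand:

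- The SAE definition carries a possibility standard, so it filters less strictly than the AE definition.
- The eCRF is not shown. A causality field cannot be called missing.
- Which set of events is the main one in an arm comparison is commonly left to the statistical analysis plan.

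A reader might infer more than the protocol supports:

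- **That the fractionation comparison is biased.** Toxicity is an endpoint as graded by CTCAE at scheduled visits, with no attribution filter stated.
- **That the independent committee sees biased arm comparisons.** No AE comparison by arm for that committee is described. AEs and SAEs go to the trial management committee.
- **That the acute toxicity analysis after 400 patients is biased.** It is not tied to AE reports, and the month 3 visit falls at about the end of the 90-day acute window.
- **That the bias can be put in percentage points.** The protocol gives no attribution rates, so any such figure would be invented. Since every arm is irradiated, unequal attribution is also less obvious than against an unirradiated control.

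**Conclusion.** The inconsistency is real and should be corrected. The AE and SAE definitions, the documentation rule and the follow-up sentence do not give one rule for what enters the AE/SAE record, and reading them together does not remove the conflict.

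The reach is limited to the AE/SAE eCRF records and the SAE reporting that depends on them. It matters most during treatment, before the month 3 visit. The CTCAE endpoints and the non-inferiority analysis are not shown to be affected. Differential recording between arms is possible, but its size and direction cannot be derived from the protocol. The concern about arm-aware judgement rests on the inference that local investigators know the allocation. The contradiction itself needs no such assumption. It should be settled in the protocol, because an analysis plan cannot restore events that were never entered.

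**What to change.** Let one rule govern recording, and treat causality as information about an event:

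1. In the AE definition, delete the condition that the symptom be caused by radiotherapy. Keep the pelvic and abdominal scope and the symptom lists.
2. In the SAE definition, delete both the related-to and the may-be-caused-by wording, leaving the seriousness criteria.
3. Align the sentence on radiation-induced SAEs in the 60 months after radiotherapy with the same rule. Changing the definitions alone would leave this conflict in place. If a narrower rule is intended for that period, say so and say who makes the judgement.
4. State that the local investigator's causality assessment, already required, is recorded as an attribute of each entered event.

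The cost is a few sentences, a check that the eCRF holds the assessment for each event, and somewhat more events for sites to record.

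### The SAE definition does not make hospitalisation a criterion of its own, although the reporting rules that follow imply that it is one

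*Protocol*

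**What the plan says.** All of the relevant text stands in the Protocol, in the sections Adverse Event (AE) and Serious Adverse Event (SAE).

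- **Definition.** An SAE is a radiotherapy-related serious event with any one of a list of results: death, "a life-threatening experience that requires hospitalization or requires intervention to prevent permanent impairment/damage". The protocol defines seriousness nowhere else.
- **Exclusions.** Later in the SAE section, "the following situations are excluded from expedited notification on a SAE form" and go on the CRF follow-up form instead. The first is "Elective hospitalisation to simplify treatment or procedures". The second begins "Elective hospitalisation for pre-existing conditions that" and goes on to require that trial treatment has not made them worse. Disease progression, and death from it, complete the list.
- **Clocks.** "All SAE must be reported to sponsor within 1 working day". The sponsor passes SUSARs to the Ethics Committee "within 7 days, if life threatening or fatal, and within 15 days, if not life threatening", and reports all SAEs to it once a year.
- **Other events.** "AEs are recorded in the eCRF"; no expedited clock is attached to them.

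**The concern.** The definition decides which events reach the sponsor within one working day, which can become SUSARs, and which appear in the annual report to the Ethics Committee. In its only mention of hospitalisation, the admission is attached to an experience that is already life threatening. An unplanned admission that is not life threatening therefore has no clear place in it. The exclusion list a few lines later carves elective admissions out of expedited notification, as if admissions were otherwise covered.

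This matters more here than in many trials. The fractionation comparison is a non-inferiority question about GI and GU toxicity. The section Potential risks for the patient accepts that more toxicity in the short arm cannot be excluded and calls careful toxicity collection important. With several centres working from one ambiguous sentence, the same admission could be an SAE at one site and an AE at another.

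**Working it through.** No arithmetic applies. The check is to set out the ways the definition can be read and see how each fits the rules that follow it.

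**Three readings**

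- **A.** Two criteria: death; a life-threatening experience that needs either hospitalisation or intervention.
- **B.** Three criteria: death; a life-threatening experience that needs hospitalisation; intervention against permanent damage.
- **C.** Four criteria: death; life-threatening experience; hospitalisation; intervention. This needs a comma after the word experience, which the text does not have.

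**Test cases**

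| Case | A | B | C |
|---|---|---|---|
| Life-threatening event with admission | SAE | SAE | SAE |
| Unplanned admission for rectal bleeding or haematuria, not life threatening, no intervention against permanent damage | not SAE | not SAE | SAE |
| Not life threatening, but intervention against permanent damage needed | not SAE | SAE | SAE |
| Does the elective-admission exclusion remove anything? | hardly | hardly | yes |
| Does the 15-day SUSAR clock have any events to cover? | no | yes, interventions | yes, interventions and admissions |

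**Reasoning**

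1. The wording supports A or B. Under both, hospitalisation alone does not make an event serious.
2. An elective admission to simplify a procedure is hardly a life-threatening event. Exempting it has a real effect only under C.
3. A SUSAR must be serious. Under A, every serious event is fatal or life threatening, so the 15-day clock would never run. It therefore speaks against A. It does not decide between B and C.
4. The second row is the core of the problem. The literal definition (A or B) leaves that admission out. The exclusion list, which exempts only elective admissions, implies that it is in. Rectal bleeding and haematuria are both on the protocol's own AE list, so the case is not far-fetched.
5. Under A or B, that admission misses three routes: the one-working-day report, the SUSAR route and the annual SAE report. It stays in the eCRF as an AE.

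**Scope.** The definition applies to every arm: 4 × 254 = 1,016 patients. The protocol gives no admission rate, so the number of affected events cannot be estimated.

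**The case against.** **The conflict is only implied.** No sentence states that hospitalisation is a criterion. The exclusion list also names disease progression, which is neither a criterion in the definition nor caused by radiotherapy, so the list is partly precautionary and an entry on it does not prove a matching criterion. This stands, and the point should not be put as an explicit contradiction. What the list and the 15-day clock show is intent, and the definition does not carry that intent.

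**It may be a lost comma.** That is plausible. It explains the sentence but does not correct it, and no other passage does.

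**Interventions may already be covered.** A reader might infer that every non-life-threatening intervention against permanent damage also falls outside. That holds only under reading A. Reading B is at least as natural, because the definition announces a list. A fistula or retention that needs such an intervention would then be an SAE already.

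**The events are not lost.** This stands. The protocol has AEs reported continuously, described in detail (onset, grade, management, outcome) and passed to the trial management committee. CTCAE grading at scheduled visits, the IDMC and the four-arm acute toxicity analysis after 400 patients add further oversight. A reader might infer that severe toxicity would go unseen; the protocol does not support that. The gap is in expedited and annual SAE reporting.

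**Severe toxicity is not predicted.** The section Organs at risk warns that very severe effects are possible, then cites low grade 2 rates and very rare grade 3 events under isotoxic constraints. The case rests on what could happen to an admission, not on an expected rate.

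**Conclusion.** The point holds as a defect in an operative safety rule. The definition does not make hospitalisation a criterion of its own and leaves the standing of the intervention criterion unclear, while the reporting rules after it imply that non-elective admissions count. The affected class is narrow: non-elective admissions for radiation toxicity that are neither life threatening nor meet the permanent-impairment criterion. For these, the expedited sponsor report, the SUSAR route and the annual SAE report depend on how a site reads one sentence.

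The size cannot be given as a number. A reader might take the three experimental arms, 3 × 254 = 762 patients, as the extent. That figure counts neither affected patients nor events, and the definition governs the reference arm as well.

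No endpoint, sample size or primary inference is touched. The conclusion assumes that sites follow the sentence as printed and that no other trial document, such as SAE form instructions, defines seriousness differently.

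**What to change.** Reconcile the definition with the reporting rules in the section Serious Adverse Event (SAE) by listing the seriousness criteria as separate items:

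- death;
- life-threatening event;
- non-elective hospitalisation;
- intervention needed to avert permanent impairment or damage.

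Keep the two elective-admission exclusions, which then have a clear function. Prolonged hospitalisation is mentioned nowhere in the protocol, so this point does not ask for it.

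The change is one sentence, concerns reporting only and alters no treatment. The cost is some additional SAE forms and sponsor reports.
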